APPENDIX A: Brigham and Women's Outpatient Cervical Ripening Protocol

Medical Staff Note...

**OBSTETRICS AND GYNECOLOGY
BRIGHAM AND WOMEN'S HOSPITAL**

DATE: 12/21/2020 **Updated June 17, 2021** # 2313

TO: Medical Staff

FROM: [name], [name], [name], [name], [name],
[name], [name], [name]

RE: **Office-Based Ambulatory Cervical Ripening Protocols**

Updates June 17, 2021

GBS positivity is no longer an exclusion for office-based ambulatory cervical ripening using a mechanical method of cervical ripening, including Foley or Cook balloons, Dilapan or laminaria cervical dilators.

Mild polyhydramnios is not an exclusion for office-based ambulatory cervical ripening.

Well-controlled GDM, with or without medications, is not an exclusion for ambulatory office-based cervical ripening.

Background: As noted in a recent Medical Staff note from [name] (**Cervical Ripening and Induction of Labor in Nulliparous Patients before Forty Weeks' Gestational Age, #2304**) clinical practice

is evolving to increase the use of office-based ambulatory cervical ripening as the **initial step** for induction of labor in low-risk women from 39 weeks and 0 days gestation through 39 weeks and 6 days gestation. **One day of office-based ambulatory cervical ripening is an important part of a multi-step process that is followed by additional ambulatory (CWN5 Triage) or inpatient cervical ripening, if needed, and oxytocin induction of labor.**

At BWH we have years of experience with office-based ambulatory cervical ripening using oral misoprostol. Office-based ambulatory mechanical cervical ripening with a balloon catheter (Foley or Cook catheters) or Dilapan (hygroscopic cervical dilator) are also effective and safe methods (Alfirevic 2020, Dong 2020, Yang 2018, Saade 2019). Mechanical methods are particularly suitable for the office-based ambulatory setting as they are not generally associated with an increased risk of tachysystole.

The choice of office-based ambulatory cervical ripening agent is at the provider's discretion. However, we encourage the following:

- (1) First line: Balloon cervical ripening (30 cc Foley or Cook balloon)
- (2) Second line: Dilapan-hygroscopic cervical dilator
- (3) Third line: Oral misoprostol

At this time, we are not endorsing the use of dual agents in the office-based ambulatory setting (e.g. balloon or Dilapan plus misoprostol).

Exclusions (all office-based ambulatory methods of cervical ripening):

Fetal conditions:

Contraindication to vaginal delivery (non-vertex presentation, complete placenta previa, etc.)
IUGR: Growth < 5th percentile
Abnormal umbilical artery dopplers
Oligohydramnios or polyhydramnios (**mild polyhydramnios is not an exclusion to ambulatory office-based cervical ripening**)
Multiple gestation
Major fetal anomalies
Induction for the indication of non-reassuring fetal assessment
Any history of decreased fetal movement
Any history of non-reassuring fetal assessment

Maternal conditions:

Prior Caesarean delivery or uterine surgery involving removal of a full thickness of uterine tissue
Clinically significant vaginal bleeding.
Type 1 or Type 2 diabetes mellitus. (**Well-controlled GDM with or without medication is not a contraindication to ambulatory office-based cervical ripening.**)
Significant hypertension: preeclampsia, or taking antihypertensive medications instituted or recently up-titrated in this pregnancy to control blood pressure.
A patient who is unable to understand instructions or return easily should symptoms arise

Exclusion specific to mechanical methods (Foley/Cook/Dilapan):

GBS positivity is no longer an exclusion to office-based ambulatory cervical ripening using a mechanical method of cervical ripening, including Foley or Cook balloons, Dilapan or laminaria cervical dilators.

Protocol: Overall, office-based ambulatory cervical ripening by any method should be followed by additional CWN5 triage cervical ripening, if needed, or by inpatient induction of labor if the cervix is favorable within 6 to 24 hours.

Important guidance: An inpatient induction of labor slot should be booked for 6 to 24 hours following the initiation of office-based ambulatory cervical ripening.

Prior to ripening (all methods):

- 1) Confirm eligibility. Review exclusion criteria above.
- 2) **Confirm that an inpatient induction slot is booked at 6 to 24 hours following the initiation of office-based ambulatory cervical ripening.**
- 3) Confirm that clinical testing such as NST or BPP is performed within the appropriate time frame (i.e. if weekly fetal testing is indicated, this should be performed within the week prior to the induction or if an ultrasound estimate of fetal weight is indicated this should be performed within 2 weeks of the induction).
- 4) Confirm cephalic presentation and normal fluid volume. This can be done via formal or bedside ultrasound. If a formal ultrasound is performed within the week but not on the day of induction, cephalic presentation should be confirmed by physical exam or bedside ultrasound.

Prior to ripening (misoprostol only):

- 1) NST must be performed and must be reactive without excessive uterine activity (no more than 2 contractions in 10 minutes).

Foley Balloon Placement:

- 1) This can be placed in any setting, though ideally in the office-based ambulatory setting in the afternoon.
- 2) Either a 30 cc Foley (inflated up to 35 cc) or a Cook catheter can be used.
- 3) Balloons can be placed digitally or with a speculum (at provider discretion). If a speculum is used, the cervix should be cleansed with betadine prior to placement.
- 4) Only 2 attempts at a balloon should be performed. If placement fails after 2 attempts, the provider can place Dilapan instead or abandon office-based ambulatory mechanical ripening.
- 5) After placement, the Foley catheter tail can be taped to the thigh, tucked into the vagina or tied off and trimmed.
- 6) No monitoring is needed after placement.
- 7) If the Foley catheter falls out before the scheduled inpatient appointment, the patient should be instructed to throw out the Foley catheter. She can stay home until her scheduled appointment (unless labor, rupture of membranes or other concerns require an office or hospital visit).

Dilapan Placement:

- 1) Cervix is visualized with a speculum and cleansed with betadine.
- 2) Dilapan rods are placed using a ring forceps. Ideally 3-5 rods should be placed. No more than 5 rods should be used. Rods can be moistened with saline or sterile water to aid in placement.
- 3) A moistened gauze can be placed in the vagina to help keep the Dilapan in place if desired (though not necessary).

- 4) The number of Dilapan and gauzes left in the patient should be clearly documented in the EPIC record.
- 5) No monitoring is needed after placement.
- 6) If the Dilapan(s) or sponge(s) fall out before the scheduled inpatient appointment, the patient should be instructed to collect all the rods/sponges in a plastic bag or take a picture of the rods/sponges and throw them away. She can stay home until her scheduled appointment (unless labor/rupture of membranes or other concerns arise).

Misoprostol Placement:

- 1) 50 mcg of oral misoprostol is administered

Appendix B: Patient Satisfaction Survey

Patients: Please consider your experience with cervical ripening, from when the device was placed until now. The answers to your questions will not affect any aspect of your care.

1. Before placement of the cervical ripening device were you anxious? (Please circle one)

1- Not at all 2- Slightly 3- Moderately 4- Very 5- Extremely

2. Did the insertion of the device cause you any discomfort? (Please circle one)

1- Not at all 2- Slightly 3- Moderately 4- Very 5- Extremely

3. What number would you rate the pain you had while the device was being placed? (scale 0-10, 0= no pain, 10= worse pain imaginable, please circle one number)

0 1 2 3 4 5 6 7 8 9 10

4. Once you went home with cervical ripening device (please circle one for each question):

A) Did you feel any discomfort?

1- Not at all 2- Slight Discomfort 3- Moderate Discomfort 4- Very Uncomfortable 5- Extremely Uncomfortable

B) Were you able to complete your routine daily activities?

1- Not at all 2- Slightly 3- Moderately 4- Very 5- Extremely

C) How able were you to get some sleep?

1- Not at all 2- Slightly 3- Moderately 4- Very 5- Extremely

5. Please rate your overall discomfort during the entire cervical ripening experience (scale 0-10, 0= no pain, 10= worse pain imaginable, please circle one number).

0 1 2 3 4 5 6 7 8 9 10

6. Please rate your overall satisfaction with the entire cervical ripening experience(scale 0-10, 0= completely dissatisfied, 10= completely satisfied, please circle one number).

0 1 2 3 4 5 6 7 8 9 10

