Clinic visit for term (37-41 6/7 week) pregnant patients 18-50 years old with decision by primary obstetrics provider for induction of labor and patient is deemed candidate for outpatient cervical ripening per BWH Cervical Ripening Protocol by their primary obstetrics provider

- Inclusion:
 - Vertex presentation
 - Induction of labor indicated for maternal or neonatal reasons
- Exclusion
 - Prior cesarean section
 - Non-English-speaking participants
 - No need for cervical ripening (Bishop score >6, >2cm dilated)

Patient is scheduled for outpatient cervical ripening per BWH protocol. Her outpatient obstetrical provider informs her of the study. Study staff will attempt to contact patient once appointment is made and discusses study with patient and answer any questions she may have. If patient is unable to be contacted they will still be approached for the study when they arrive for outpatient cervical ripening after study has been introduced by a clinician/provider at their visit.

At time of her cervical ripening appointment on CWN 3, CWN 5 labor and delivery, or at [name] if patient remains interested, she is consented by physician investigators. Questions answered.

RANDOMIZATION: 1:1 Cook catheter Vs Dilapan-S per outpatient protocol.

Cervical ripening with either agent per randomization.

If unable to place cervical ripening device, further cervical ripening per provider preference by one of options already approved per BWH outpatient cervical ripening protocol

Return to L&D within 24hrs of device placement (return visit will be scheduled through hospital EMR as is current BWH outpatient cervical ripening protocol) or earlier with any concerning symptoms (vaginal bleeding, fever, rupture of membranes, labor, decreased fetal movement, etc), as detailed in existing BWH outpatient cervical ripening protocol

When returned to L&D, device removed or confirmed expelled. Sterile vaginal exam performed by blinded examiner (3rd year, chief resident, or further in training- i.e. Fellow or Attending), blinded to study arm.

Paper patient satisfaction survey to be given to patient at this time by study staff for written completion by subject

Further induction of labor per primary labor and delivery team.

4. Subject Selection

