study staff will then discuss the study in more detail, answer any questions, then will step away while NST is being performed (20-30 minutes) to allow for contemplation then will re-approach the subject to confirm if they are or are not interested in the study after NST is complete. After it is confirmed that the patient is still candidate for outpatient cervical ripening per standard practice at Brigham and Women's, which requires the non-stress test fetal heart tracing to be reactive, an exam to confirm the cervix needs ripening (Bishop score < 6 and cervix < 2cm dilated) and an ultrasound to confirm cephalic presentation, they will be randomized to either Dilapan-S or Cook balloon in a 1:1 ratio.

At the time of enrollment, patients will be assured that they will receive standard of care treatments whether or not they are in the study and enrollment will not affect their care.

Only adults will be included in the study. Study will be limited to English speaking patients as enrollment may happen day or night and on weekends (given outpatient cervical ripening schedule on labor and delivery) when interpreters may not be available. No surrogate decision makers will be allowed to consent for patients.

A random number generator will be used to randomize women in blocks of 6 with stratification based on parity (patients who have had a vaginal delivery before or not).

As randomization will occur after sterile vaginal exam, the examiner obtaining the initial exam will be blinded to which arm of the study the patient will be in as the exam will be recorded prior to randomization. The patient will not be blinded as the devices are different in placement and post-placement.

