6. STUDY PROCEDURES

Upon presentation for cervical ripening, a non-stress test will be performed per BWH outpatient ripening protocol. Then a sterile vaginal exam will be completed to assign Bishop score, as per standard routine. A bedside ultrasound will be completed to confirm fetus is still in the vertex presentation. The patient will then be consented if they have a reactive non-stress test, a Bishop score <6 and cervical exam <3cm dilated with confirmed vertex fetus. Once the patient has been consented and randomized, the participant will have a Cook catheter or Dilapan-S by direct visualization with a speculum, For the Cook catheter, the uterine component of the balloon will be inflated to maximum 60mL, the vaginal balloon will not be inflated per standard practice at BWH and per the literature that shows slightly increased pain and negligible improvement in cervical ripening. The catheter will be taped to the inner thigh with gentle traction. For Dilapan-S, 3-5 dilators will be placed per BWH protocol.

After placement, the patient will be discharged home with strict return precautions per the BWH outpatient cervical ripening protocol. With written instructions of who to call/page, with phone number listed, list of concerns that should prompt calling / return to hospital: Fever > 100.4 Fahrenheit, labor, rupture of membranes, reduced fetal movement vaginal bleeding, what to do if the balloon/rods fall out, exact time and place to return. Patients must return to labor and delivery within 24 hours of cervical ripening agent placement at their scheduled inpatient induction time.

Upon return to labor and delivery, if not already expelled, the mechanical ripening device will be removed, and an examiner **blinded to the cervical ripening method** will complete a sterile vaginal exam to assign a Bishop score.

The patient satisfaction survey will be completed by the patient at this time in paper form and collected by study staff.

At that point health care providers will manage active labor per usual practice. Labor interventions are at the discretion of the healthcare provider. The need for operative delivery or cesarean section will be at the discretion of the healthcare provider.

Secondary outcome information will be obtained from the Epic record including delivery, maternal and neonatal outcomes as defined in the statistical analysis below.

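### Anxiety before placement and discomfort and pain at insertion are asked about only after ripening, which exposes three secondary survey items to avoidable recall and carry-over

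*Combined protocol and SAP*

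**What the plan says.** Timing. In the Section 3 study flow, after device removal or confirmed expulsion and the blinded exam: "Paper patient satisfaction survey to be given to patient at this time by study staff for written completion by subject". Section 6 repeats this after the post-ripening exam: "The patient satisfaction survey will be completed by the patient at this time in paper form and collected by study staff". Section 6 requires return within 24 hours of placement. It also lets a form missed during the delivery admission be collected up to the 6-week postpartum visit, and Section 9 repeats that limit. No anxiety or pain rating is planned at the placement visit.

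Content. The Appendix B instruction reads "Please consider your experience with cervical ripening, from when the device was placed until now". Item 1 asks "Before placement of the cervical ripening device were you anxious" (1 to 5). Item 2 asks "Did the insertion of the device cause you any discomfort" (1 to 5). Item 3 asks "What number would you rate the pain you had while the device was being placed" (0 to 10). Items 4A to 4C concern the time at home, item 5 overall discomfort and item 6 overall satisfaction.

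Blinding. Section 5: "The patient will not be blinded as the devices are different in placement and post-placement". Only the examiners are blinded, which protects the Bishop score and not the survey. Section 6 places randomization before placement.

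**The concern.** Aim 2 compares how women experience two openly different devices, with a stated expectation that Dilapan-S will be preferred. The survey divides that experience into before placement, insertion, home and overall, but asks about all four at one late sitting. Answers about the first two periods can be coloured by what followed: learning the allocation, the time at home with the device and, on a late form, labor and delivery.

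At stake is how an arm difference on items 1 to 3 could be read. For item 1 it might reflect chance imbalance, reaction to the allocation, or recall. For items 2 and 3 it might reflect insertion itself or discomfort felt later. A rating not taken at placement cannot be recovered in the analysis.

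**Working it through.** The plan states no figure on this point, so there is none to reproduce. The check sets Sections 3, 5, 6 and 9 against Appendix B, with two counts and one illustration.

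**1. Order of events (Sections 3, 5 and 6).** Non-stress test, cervical exam and ultrasound; consent; randomization; placement attempt; home; return within 24 hours; removal or confirmed expulsion; blinded exam; survey. The fallback for a missed form extends to the 6-week postpartum visit.

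**2. What lies between the period asked about and the answer.**

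| Item | Period asked about | What intervenes |
|---|---|---|
| 1 | Before placement | Allocation, placement, home period; possibly delivery |
| 2, 3 | Placement | Home period; possibly delivery |
| 4A, 4B, 4C | Home | Removal and exam; possibly delivery |
| 5, 6 | Whole ripening experience | Can only be asked afterwards |

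Rated responses: items 1, 2, 3, 4A, 4B, 4C, 5 and 6 make 8. Those that look back to placement or earlier: 3 of 8.

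**3. Item 1.** The instruction starts the recall window at placement, so item 1 asks about a time outside the form's own window. The time before placement also includes the time after randomization, so the item can take in a woman's reaction to learning her device even if her recall is perfect.

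**4. Items 2 and 3.** The delay applies in both arms. A between-arm bias needs it to act differently by arm, for example if one device is more uncomfortable at home and its insertion rating is pulled up with it. That is plausible with unblinded patients, but the documents do not show it.

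**5. Failed placements.** Section 9 cites a 10% failure rate from prior studies. If it applied here, 0.10 × 90 = 9 women. Section 3 then allows another approved method, and Appendix A allows Dilapan after two failed balloon attempts. At return, items 2 and 3 do not say which attempt is meant. A rating taken right after the allocated attempt does.

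**6. Illustration on assumed values.** Suppose there is no true difference in insertion pain, 45 women per arm all answer item 3, and recall shifts one arm by b points, with standard deviation s. A normal approximation for means stands in for the planned non-parametric analysis:

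SE = s√(2/45); P(two-sided p < 0.05) = 1 − Φ(1.96 − b/SE) + Φ(−1.96 − b/SE).

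| s | SE | b = 0.5 | b = 1 |
|---|---|---|---|
| 2 | 0.422 | 0.220 | 0.660 |
| 2.5 | 0.527 | 0.158 | 0.475 |
| 3 | 0.632 | 0.124 | 0.353 |

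Neither b nor s comes from the documents. The table shows only that such a shift would matter if it occurred.

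**The case against.** The strongest reply is that this is a preference about questionnaire design. Aim 2 is about satisfaction; item 6 measures it directly, and items 5 and 6 are correctly asked afterwards. Sections 2 and 9 do not name items 1 to 3 as separate outcomes. Items 2 and 3 are explicitly anchored to insertion, and item 4A gives home discomfort its own place. The delay is common to both arms, and the size of any differential effect is unknown. A change made mid-trial would leave items 1 to 3 measured in two ways within 90 women.

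Most of this stands and limits the point. Three stronger readings do not hold:

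- A reader might infer that the plan relies on item 1 as a baseline and that this fails. No section calls it a baseline or covariate; the only planned adjustment is for parity.
- A reader might infer that items 2 and 3 cannot separate insertion from home. The documents show exposure to carry-over, not an inability to separate.
- A reader might infer that the same carry-over reaches all 90 women after a night at home. Women whose placement failed may not go home with the allocated device, and Appendix A books the induction slot 6 to 24 hours after ripening starts.

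The reply does not answer the mismatch between item 1 and the form's recall window, the fact that item 1 can absorb reaction to the allocation, or the late collection window. All three can be avoided for items 1 to 3 at a visit that study staff already attend.

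**Conclusion.** The point holds as a cheap improvement to three secondary survey items. Items 1 to 3 are answered up to 24 hours after placement on the planned schedule, and possibly as late as the 6-week postpartum visit, by women who know their device. The resulting recall and carry-over may differ by arm; the direction and size are unknown.

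A reader might infer that Aim 2 as a whole is compromised. The documents do not support that: the overall ratings that best address it (items 5 and 6) are properly asked afterwards, and the primary outcome rests on blinded exams. Nor would retiming blind anyone. Ratings of insertion stay unblinded whenever they are taken; what is removed is home-period and delivery recall from items 2 and 3, and allocation and device experience from item 1.

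The conclusion assumes that Appendix B is the only patient-reported form, as the document indicates.

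**What to change.** Split Appendix B into two paper sheets.

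- **Placement visit.** Item 1, reworded as current anxiety, completed after consent and before the allocation is revealed. Items 2 and 3 completed right after the allocated placement attempt, successful or not, and before discharge home.
- **Return to labor and delivery.** Items 4 to 6 as now, with the completion date recorded so that late forms can be identified.

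Do not use the non-stress-test wait for item 1. Section 5 sets those 20 to 30 minutes aside for the woman to consider taking part, and Section 6 places consent after a reactive test, so data would be collected before consent.

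Report item 1 as a baseline descriptor and not as a satisfaction outcome. Report items 2 and 3 as unblinded ratings of the allocated placement attempt.

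Cost: a minor amendment and about two minutes of staff time per woman. Items 1 to 3 on forms already collected under the single-sheet layout must be flagged and reported separately, which reduces the number of comparable answers on those items.

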Secondary maternal outcomes will be measured including patient satisfaction with cervical ripening method via a survey administered after return to labor and delivery (Appendix B), cesarean delivery rate, time from admission on labor and delivery to delivery, maternal length of stay, and indication for cesarean delivery. We will also calculate a composite cervical ripening success score. Success will be defined by a lack of any of the following: failure of placement of cervical ripening agent, unscheduled return to medical care, rupture of membranes, vaginal bleeding, or need for further cervical ripening after the initial agent is removed. We will also calculate a composite maternal morbidity outcome. Morbidity will be defined by any of the following: higher-order laceration, blood transfusion, endometritis, wound infection, venous thromboembolism, hysterectomy, ICU admission or death. These outcomes will also be stratified by parity. We will also evaluate rates of regional analgesia use in both groups.

A composite neonatal morbidity will be calculated including any one of the following: culture-proven neonatal sepsis, neonatal blood transfusion, hypoxic-ischemic encephalopathy, intraventricular hemorrhage grade 3 or 4, or therapeutic hypothermia. We will also analyze NICU admission, NICU admission for greater than 48 hours, and neonatal length of stay.

This study design is a non-inferiority randomized control trial with 1:1 randomization comparing Dilapan-S to Cook Catheter with the primary outcome of change in Bishop score. We have defined a non-inferiority margin of 2 with a standard deviation of 3 consistent with prior literature. A Type I α error of 0.05 was selected. Assuming 80% power and a two-sided P value we would need 39 patients in each arm for a total of 78 patients; however, prior studies⁶ reported a 10% failure of placement rate (due to patient intolerance of exam or provider failure) to account for this and the small risk of loss to follow-up, we will increase the sample size by 15% and will include 45 participants in each group for a total of 90 participants.

For statistical purposes, intent to treat analysis will be performed. Non-parametric measures will be used for statistical analysis. These models will also be adjusted for parity.

10. Monitoring and Quality Assurance

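### Survey item 4 (home discomfort, activities, sleep) has no 'does not apply' choice and no expulsion question, so some answers and blanks cannot be interpreted

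*Combined protocol and SAP*

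**What the plan says.** Section 9 lists "patient satisfaction with cervical ripening method via a survey administered after return to labor and delivery" among the secondary maternal outcomes, and Specific Aim 2 (Section 2) rests on that survey. No item or score is named, and there is no rule for items that do not fit a woman's course. The analysis is by intention to treat with non-parametric methods.

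In Appendix B, item 4 begins "Once you went home with cervical ripening device (please circle one for each question". Its three parts are "Did you feel any discomfort" (4A), "Were you able to complete your routine daily activities" (4B) and "How able were you to get some sleep" (4C), each scored 1 to 5. The introduction to the survey sets the reference period as placement of the device up to completion of the form. Item 6 asks separately for overall satisfaction, 0 to 10.

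Other parts of the plan describe who will receive this form:

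- **Time at home.** Section 3 requires return within 24 hours and sets no minimum. Appendix A says "An inpatient induction of labor slot should be booked for 6 to 24 hours following the initiation of office-based ambulatory cervical ripening". Section 5 notes that "enrollment may happen day or night and on weekends". Sections 3 and 6 also provide for early return with symptoms.
- **Expulsion.** Section 6 foresees that a device may already be out on return. Appendix A covers the event for the balloon ("If the Foley catheter falls out before the scheduled inpatient appointment") and, in a parallel item, for Dilapan. In both cases the woman may remain at home until her appointment.
- **Placement failure.** Section 9 cites a 10% rate. Section 3 then allows another approved method, at the provider's choice.

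**The concern.** The form tells each woman to circle an answer to every part of item 4, but for some women no answer is true. A woman who went home with no device has nothing to report on 4A. A woman placed in the morning and back by evening may have had no sleep period for 4C. An evening placement with a morning return may leave no ordinary daytime for 4B. If she follows the instruction, the lowest category is the nearest literal fit to 4B or 4C, and it is the same code as that of a woman whose device kept her awake or inactive. If she leaves the part blank, the blank looks like any other missing answer.

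Expulsion raises a related problem. The answers of a woman whose device came out early mix hours with and without it, and the form does not record that this happened.

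Item 4B has a separate wording fault: it asks a yes/no question but offers degrees up to 'Very' and 'Extremely'.

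At stake are the only three survey items specific to time at home, in a trial of outpatient ripening. The missing information cannot be reliably recovered once the forms are collected.

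**Working it through.** The documents give no figure for the survey, no expulsion rate and no distribution of placement or return times. The only planned sizes are those for the primary outcome.

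1. **The plan's own numbers (Section 9).** With margin 2, SD 3, two-sided 0.05 and 80% power, the normal formula gives 2 × (3 × (1.960 + 0.842) / 2)² = 35.3, so 36 per arm. The t-test version gives 37. Adjusting the t version for a Wilcoxon test (efficiency 3/π = 0.955) gives the stated 39. Then 39 × 1.15 = 44.85, so 45 per arm and 90 in all.

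2. **Placement failures.** 10% × 90 = 9 women, leaving 81 (40.5 per arm). A woman who then goes home on another method answers item 4 about that method, or has no device to answer about.

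3. **Cost in precision of setting them aside.** The detectable difference at 80% power, in SD units, is (1.960 + 0.842) × √(2/n). For n = 45 it is 0.59. For n = 40.5 it is 0.62. If a further 10%, 20% or 30% answered 'does not apply' (assumed rates), n per arm would be about 36.5, 32.4 or 28.3 and the detectable difference 0.66, 0.70 or 0.74 SD.

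4. **Noise if the affected shares are equal.** If a share q in each arm gives answers unrelated to the device, a true difference shrinks by the factor 1 − q. That is 0.9 at q = 10% and 0.7 at q = 30% (assumed).

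5. **How common a same-day return might be.** Assume return by 23:00 as a rough marker and time at home uniform over 6 to 24 hours. For placement uniform over 08:00–17:00, the average of (17 − placement hour)/18 is 4.5/18 = 25%. For 12:00–17:00 it is 2.5/18 = 14%. For 12:00–17:00 with 12 to 24 hours at home it is 0%. The share depends entirely on the assumption. It also says nothing about a difference between arms.

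6. **Bias if the shares differ.** If affected women score g points away from what they would otherwise have circled, and their share differs between arms by p, the false difference in means is g × p. With assumed g from 0.5 to 2 points and p from 10% to 40%, it runs from 0.05 to 0.8 points, and it is 0 when p = 0. For placement failure alone, if all 9 expected failures fell in one arm, p = 9/45 = 20%, which gives 0.1 to 0.4 points over the same range of g. For scale, if the item SD were 1 (assumed), the standard error of a difference is √(2/45) = 0.21. The planned analysis is non-parametric, so these mean shifts are only illustrative.

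**The case against.** There is a fair case that this is little more than polish, and much of it stands.

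- **Booked return times should balance.** Appendix A has the inpatient slot confirmed before ripening starts, and Section 6 has women return at that scheduled time. Scheduled time at home is therefore essentially fixed before the device is placed, and randomisation should balance it. A reader might infer from the 6-to-24-hour window that the arms will be biased; the documents do not support that. Only events after randomisation (placement failure, unscheduled return, expulsion) could differ by device.
- **The form does not presume a day and a night.** A reader might infer that it scores every woman as if she had both. It mentions neither, 4A needs no night, 4C asks only about some sleep, a paper item can be left blank, and no scoring rule exists.
- **Expulsion is part of the experience.** A reader might infer that answers after expulsion do not measure the device. They still cover the hours in place, and the survey period together with intention to treat makes later, device-free hours part of the experience with the method. Restricting 4A–4C to the time in place would change the question asked, and is not proposed here.
- **Other data exist.** Unscheduled return enters the composite success outcome, and expulsion status is established on return (Section 3). The form still does not capture when the device came out or whether an item applied.

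What the objection does not answer is that the instruction to circle every part, with no way to say it does not apply, produces answers and blanks whose meaning is unknown.

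**Conclusion.** The point holds as a limited measurement fault in Appendix B. About 9 of 90 women, at the plan's own 10% rate, have no home period with the assigned device. An unknown further number may have had no sleep period or daytime at home, or a device that came out early. The main effect is noise in three secondary items. A between-arm bias is possible through placement failure, unscheduled early return or expulsion, but the documents do not allow its size to be estimated; the point shifts above rest on assumed inputs and only show scale.

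It would go too far to conclude that Aim 2 is undermined. Item 6 asks about overall satisfaction directly and does not depend on item 4's stem. The primary outcome and the sample size are untouched. Minor priority.

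**What to change.** In Appendix B:

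- Add a 'does not apply' choice to 4A, 4B and 4C for women who did not go home with the device. On 4B let it also cover no daytime at home, and on 4C no sleep period at home.
- Add a question on whether the device came out before return and, if so, at about what time.
- Put 4B in the 'how able' form that 4C already uses, so that it fits its answer scale.
- Keep the survey's existing reference period.

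In Section 9, add that 4A–4C are analysed among women to whom they apply, that 'does not apply' and expulsion counts are reported by arm, and that these comparisons are made in a group defined after randomisation. The same sentence should say how women sent home on a method other than the assigned one are counted.

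The cost is a small edit to a paper form and a short addition to the analysis text. The downside is that these three items lose the full protection of randomisation and a little precision, which is why the counts by arm must be shown.
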